#### **8.4.6 Ischemic events and rate of rescue medication during the study**

Combined clinical endpoints for ischemic events (myocardial infarction and ischemic stroke/TIA) and rate of rescue medication (additional anti-platelet co-medication) during the study will be analyzed comparing groups for

- incidence of events adjusted for application of rescue medication during the study (yes/no)

using the Cochran-Mantel-Haenszel procedure.

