7.2.5. Assessment of adverse events

Adverse events will be closely monitored including any unexpected effects on cerebral or myocardial ischemia and bleeding events. Wound healing complications will be documented as part of general adverse event reporting (see also section 8).

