9.3. Statistical Procedures

Safety

The number and proportion of patients experiencing each type of event will be summarised per treatment group. Only treatment-emergent events will be included in the analysis (i.e. those that began or worsened after screening (visit 1)).

The incidence and event (or event grouping) will be summarised and compared between treatment groups using Pearson's chi-squared tests.

Blind Review/Final Statistical Analysis Plan

A blinded review of the data shall be performed within the framework of the requirements of the ICH Guideline E9. The Blind Review Report will include the final statistical analysis plan (updated statistical analysis plan) and the final definition of data sets. If the blind review suggests changes to the principal features stated in the protocol, these should be documented in a protocol amendment.

The Blind Review Report will be finalised before the blind will be broken. Formal records shall be kept of when the statistical analysis plan was finalised as well as when the blind was subsequently broken.

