## 2. STUDY OBJECTIVES

The efficacy endpoints are:

- to evaluate whether the incidence of preoperative microembolic signals (MES) is reduced in patients with symptomatic carotid artery stenosis who have been treated with Revacept plus antiplatelet therapy (aspirin or clopidogrel) versus antiplatelet therapy alone (placebo) prior to carotid endarterectomy (CEA) or carotid artery stenting. MES will be assessed by transcranial Doppler (TCD) examination (before and after treatment).
- Rate of MES per hour (before and after treatment)
- Assessment of neurological status (NIH Stroke Scale)
- Cerebral lesion analysis by DWI-NMR and correlation to neurological status (before and after treatment and CEA or stenting)
- Clinical endpoints will be summarised cumulatively i.e. before treatment, one and three days after treatment, at 3 months and at 12 months. The following endpoints will be recorded:
  - Rate of all cause death
  - Rate of stroke-related death
  - Any TIA or stroke including haemorrhagic stroke
- Assessment of cardiovascular outcome including myocardial infarction and re-intervention up to 3 and 12 months
- Combined clinical endpoints for ischemic events (myocardial infarction and ischemic stroke/TIA) and rate of rescue medication (additional anti-platelet co-medication) during the study

Safety will be summarised by treatment group and include the following:

- Vital signs
- ECG parameters
- Anti-drug antibody titres
- Reporting AEs including wound healing complications, laboratory abnormalities and use of concomitant medication
- Haemostasis will be closely monitored by assessing:
  - laboratory parameters indicating thrombocytopenia and bleeding according to the RELY study group criteria
  - where feasible: in vitro platelet function with collagen, TRAP and ADP-mediated platelet aggregation and in vitro bleeding time by PFA-100 / PFA-200

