## 4. STUDY VARIABLES

### 4.1 Efficacy endpoints

- to evaluate whether the incidence of preoperative microembolic signals (MES) is reduced in patients with symptomatic carotid artery stenosis who have been treated with Revacept plus antiplatelet therapy (aspirin or clopidogrel) versus antiplatelet therapy alone (placebo) prior to carotid endarterectomy (CEA) or carotid artery stenting.  
MES was assessed by transcranial Doppler (TCD) examination (before and after treatment).
- Rate of MES per hour (before and after treatment)
- Assessment of neurological status (NIH Stroke Scale)
- Cerebral lesion analysis by DWI-NMR and correlation to neurological status (before and after treatment and CEA or stenting)
- Clinical endpoints will be summarised cumulatively i.e. before treatment, one and three days after treatment, at 3 months and at 12 months. The following endpoints will be recorded:
  - Rate of all cause death
  - Rate of stroke-related death
  - Any TIA or stroke including haemorrhagic stroke
- Assessment of cardiovascular outcome including myocardial infarction and re-intervention up to 3 and 12 months
- Combined clinical endpoints for ischemic events (myocardial infarction and ischemic stroke/TIA) and rate of rescue medication (additional anti-platelet co-medication) during the study

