### 8.4.1 Reduction of incidence of preoperative microembolic signals

This endpoint is to evaluate whether the rate of patients with incidence of preoperative microembolic signals (MES) was reduced (from Visit1 to Visit 3). Compared will be patients who have been treated with Revacept plus antiplatelet therapy (aspirin or clopidogrel) versus antiplatelet therapy alone (placebo) prior to carotid endarterectomy (CEA). MES data from the central reading lab ([name], Münster) are evaluated.

The evaluation will be performed using a two-sided test of superiority. Groups will be compared for the combined centers using Fisher's exact test.

The sequence of a priori defined hypotheses, with  $\pi$  rate of patients with MES V3 < MES V1 for the specified group, will be:

1)  $H_{01}: \pi_{\text{Revacept 120 mg}} = \pi_{\text{Placebo}}$  VS.

$H_{A1}: \pi_{\text{Revacept 120 mg}} > \pi_{\text{Placebo}}$

2)  $H_{02}: \pi_{\text{Revacept 40 mg}} = \pi_{\text{Placebo}}$  VS.

$H_{A2}: \pi_{\text{Revacept 40 mg}} > \pi_{\text{Placebo}}$

3)  $H_{03}: \pi_{\text{Revacept 120 mg}} = \pi_{\text{Revacept 40 mg}}$

$H_{A3}: \pi_{\text{Revacept 120 mg}} > \pi_{\text{Revacept 40 mg}}$

4)  $H_{04}: \pi_{\text{Revacept 120 mg + 40 mg}} = \pi_{\text{Placebo}}$  VS.

$H_{A4}: \pi_{\text{Revacept 120 mg + 40 mg}} > \pi_{\text{Placebo}}$

Each hypothesis will be tested using Fisher's exact test.

With the first two and the last of hypotheses the test product for a given dose level or overall will be tested against Placebo. With the third hypothesis the higher dose level of the test product will be compared against the lower dose of the test product.

Statistical Analysis Plan  
Test product: Revacept  
EudraCT number: 2011-001006-10  
Date 10.06.2019

All tests will be interpreted exploratively.

The between group risk difference and its 95% confidence interval (CI) will be estimated for each group comparison.

The prime analysis will be based on the ITT population. The PP population will be used for the supportive analyses.

In a subgroup analysis, only patients will be compared who did not receive any change in the concomitant medication with anti-platelet activity (=rescue medication) between the initial assessment at V1 and the follow-up investigation at V3 / V5.

Additionally the prevalence / rate of patients with microembolic signals (>0) at Visit 3 will be compared in a similar manner as in the hypothesis 1- 4

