#### **8.4.5 Clinical endpoints summarised cumulatively i.e. before treatment, before CEA, 1 day after CEA, at 3 months and at 12 months.**

For the following endpoints

- Rate of all cause death
- Rate of stroke-related death
- Any TIA or stroke including haemorrhagic stroke
- Rate of Myocardial infarctions and coronary re-intervention

the number of patients will be summarized by means of frequency tables. Groups will be compared using Fisher's exact test.

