## **8.6 Change in concomitant medication**

- Change in concomitant medication will be described presenting
  - number and percent of patients with new concomitant medication - taken first time after start of treatment (during the course of the study)
  - number and percent of patients with changes of pre-existing concomitant medication according to
    - dose increased
    - dose decreased
    - discontinued
  - type of medication

Statistical Analysis Plan  
Test product: Revacept  
EudraCT number: 2011-001006-10  
Date 10.06.2019

- type of medication by indication  
and summarized by means of frequency tables.

- Change in concomitant rescue medication with anti-platelet or anti-thrombotic effects.

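### SAP 8.4.6 compares the ischaemic composite only within strata of rescue antiplatelet use, which arises after randomisation; no comparison by randomised arm is named

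*SAP*

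**What the plan says.** SAP 2 and 4.1 list two linked efficacy items: "Combined clinical endpoints for ischemic events (myocardial infarction and ischemic stroke/TIA") and the "rate of rescue medication (additional anti-platelet co-medication) during the study". SAP 8.4.6 then gives the only analysis that names this composite: "incidence of events adjusted for application of rescue medication during the study (yes/no"), using the CMH procedure. It states no arm contrasts, no effect measure and no cut-off beyond the study period as a whole.

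Rescue is described differently elsewhere in the SAP. Section 8.4.1 (and likewise 8.4.2 and 8.4.4) builds a subgroup on "any change in the concomitant medication with anti-platelet activity (=rescue medication"). Section 8.6 lists "Change in concomitant rescue medication with anti-platelet or anti-thrombotic effects". Protocol 6.3 lets co-medication change with clinical need.

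The nearest unadjusted comparisons are these:

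- SAP 8.4.5 applies Fisher's exact test to separate endpoints, among them any TIA or stroke with haemorrhagic stroke included, and "Rate of Myocardial infarctions and coronary re-intervention".
- Protocol 9.3, under Safety, says of adverse events: "The incidence and event (or event grouping) will be summarised and compared between treatment groups", by Pearson's chi-squared test. Protocol 7.2.5 includes "any unexpected effects on cerebral or myocardial ischemia and bleeding events" in adverse-event monitoring.

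**The concern.** The randomised comparison is lost when patients are sorted by something that happens after treatment. Revacept could change how often antiplatelet drugs are added, and an ischaemic event could itself lead to their being added. The yes/no flag carries no time order, so a patient given rescue because of the counted event falls in the rescue stratum. The stratified odds ratio then compares patients selected partly on their outcome and partly on their response to treatment.

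Rescue use is also an endpoint in its own right. The opening sentence of SAP 8.4.6 implies that it will be compared between arms, but no test is named for it.

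SAP 8.4 reads all tests descriptively. Whatever effect measure is reported from 8.4.6 would therefore be the result for this composite, and a reader would take it as the treatment effect.

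**Working it through.** **Is there an as-randomised comparison anywhere?**

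- SAP 8.4.5: the stroke item includes haemorrhagic stroke and the MI item includes coronary re-intervention. Because of those extra events, and because a patient can have both event types, the composite cannot be rebuilt from the two tests.
- Protocol 3 and 7.2.6: the composite is not listed.
- Protocol 9.3, Safety: this could cover a grouping of ischaemic adverse events. But Protocol 7.1 schedules adverse events only to visit 6, SAP 7.6 restricts safety data to description, and SAP 8.5.4 plans frequency tables with no test.
- SAP 7.4 to 7.6 and the opening of 8.4: general rules only.

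So none is named.

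**Do the flag and the events cover the same period?** Protocol 7.1 schedules concomitant medication at visits 1 to 6. The 12-month call (7.1.7) collects clinical outcome only. If 12-month events count, the flag stops short of them.

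**Size.** The plan gives no event rate, rescue rate or expected result for this composite, so there is no figure to reproduce. All rates below are assumptions. The nearest documented figure is recurrent stroke of 30–35% over 5 years (Protocol 2). At constant risk (assumed) that is 1 − 0.70^(1/5) = 6.9% to 1 − 0.65^(1/5) = 8.3% per year; TIA and MI would add to it. With 50 patients per arm (SAP 3.3), pooled Revacept against placebo is 100 v 50.

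Let rescue after an event be e in both arms (50, 70 or 90%), and rescue in event-free patients be n₁ on Revacept and n₀ on placebo. Then:

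- OR in the rescue stratum = true OR × n₀/n₁
- OR in the no-rescue stratum = true OR × (1 − n₀)/(1 − n₁)

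If n₁ = n₀, both equal the true OR and there is no bias. If they differ, both strata are wrong and the Mantel-Haenszel (MH) average is generally biased.

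Worked case: no drug effect, 15% events, e = 70%, n₁ = 10%, n₀ = 15%. Expected counts are:

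| Stratum | Revacept event / none | Placebo event / none | N |
|---|---|---|---|
| Rescue | 10.5 / 8.5 | 5.25 / 6.375 | 30.625 |
| No rescue | 4.5 / 76.5 | 2.25 / 36.125 | 119.375 |

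- Unadjusted OR = (15 × 42.5)/(85 × 7.5) = 1.00.
- MH numerator = 10.5 × 6.375/30.625 + 4.5 × 36.125/119.375 = 2.186 + 1.362 = 3.548.
- MH denominator = 8.5 × 5.25/30.625 + 76.5 × 2.25/119.375 = 1.457 + 1.442 = 2.899.
- MH OR = 3.548/2.899 = 1.22.

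Over e = 50–90% (CMH rejection at two-sided 5%, 200,000 simulated trials per scenario):

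| Events, placebo v Revacept | True OR | n₁ v n₀ | MH OR | CMH rejection |
|---|---|---|---|---|
| 15% v 15% | 1.00 | 10% v 15% | 1.14–1.37 | 6–8% |
| 15% v 15% | 1.00 | 10% v 20% | 1.25–1.72 | 7–15% |
| 15% v 15% | 1.00 | 15% v 10% | 0.73–0.89 | 6–7% |
| 8% v 8% | 1.00 | 10% v 15% | 1.16–1.40 | 5–7% |
| 8% v 8% | 1.00 | 10% v 20% | 1.29–1.78 | 7–12% |
| 8% v 4% | 0.48 | 10% v 15% | 0.56–0.68 | – |
| 25% v 10% | 0.33 | 10% v 15% | 0.38–0.46 | – |

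The true ORs are (0.04/0.96)/(0.08/0.92) = 0.48 and (0.10/0.90)/(0.25/0.75) = 0.33.

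Power when n₁ = n₀ (10% or 20%), where the OR is unbiased and type I error is about 5%. The unadjusted tests are by exact enumeration:

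| Events | Chi-square | Fisher | CMH |
|---|---|---|---|
| 25% v 10% | 68% | 61% | 39–64% |
| 20% v 10% | 41% | 34% | 23–38% |
| 8% v 4% | 18.5% | 15.7% | 14.0–18.5% |

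**The case against.** The strongest reply is that little is lost in practice. SAP 7.6 summarises binary data by counts and percentages, so crude incidence by arm would probably be tabulated. SAP 8.4.5 tests, without adjustment, endpoints that between them contain every event in the composite. SAP 8.4.6 names a procedure rather than an odds ratio. Bias needs rescue in event-free patients to differ by arm, and no passage suggests that it would in a double-blind, single-infusion trial.

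The bias is also small against the noise at low event rates. With 4/50 v 8/100, the standard error of the log OR is √(1/4 + 1/46 + 1/8 + 1/92) = 0.64, so the 95% interval around an OR of 1.00 is about 0.29 to 3.5. Nor does the remedy buy power: at 8% v 4%, CMH beats Fisher's test in five of the six rescue scenarios.

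Much of this stands. The size is unknown, the power argument is weak at low event rates, and the differing descriptions of rescue are partly loose terminology, since 8.4.6 carries its own. But a crude table is not a named comparison, the 8.4.5 endpoints are different endpoints, and wide intervals do not make a stratified odds ratio estimate the right quantity. Equal rescue use across arms cannot be assumed when the plan lists rescue use as an efficacy endpoint.

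**Conclusion.** The point holds. For this composite the plan states one comparison, conditional on a post-randomisation variable that is itself an endpoint, and none by randomised arm. Under the assumed rates a true OR of 1.00 is estimated at 1.14–1.78 when event-free rescue is less common on Revacept, and at 0.73–0.89 (15% events) when it is more common. A true OR of 0.48 is estimated as 0.56–0.68. If rescue given event status is the same in both arms, there is no bias, and the power loss matters mainly at high event rates with rescue strongly tied to events. The documents do not show which case applies, so neither the direction nor the size of bias in this trial can be stated. Because the study is exploratory, the consequence is a reported estimate that may mislead, not a false confirmatory claim. It should be corrected.

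**What to change.** In SAP 8.4.6:

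1. Make the main comparison of the composite unadjusted, by randomised arm, in the SAP's ITT set. Use Fisher's exact test (as in 8.4.5) and a risk difference with 95% CI (as in 8.4.1) for 40 mg v placebo, 120 mg v placebo and pooled Revacept v placebo, cumulatively at 3 and 12 months. If the contrasts are to match 8.4.1, add 120 mg v 40 mg.
2. Use one definition of rescue for analysis, the one already in 4.1 and 8.4.6.
3. Compare rescue use between arms as its own outcome with Fisher's exact test to visit 6, and state that concomitant medication is not scheduled at visit 7.
4. Keep the rescue-stratified CMH as a labelled supplementary analysis at 3 months, where the flag and the events cover the same period.

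The cost is SAP wording only: the methods are already in the SAP and the data are already scheduled for collection. Fisher's test gives up some power against an uncorrected chi-square (61% v 68% at 25% v 10% events), and at low event rates against CMH in most scenarios. The gain is an estimate that can be read as the effect of randomised treatment.

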### **8.5 Assessment of safety**

Safety outcome between groups and between placebo and the combined Revacept groups will be compared.

#### **8.5.1 Vital signs**

Vital signs were assessed at Screening (Visit 1, Baseline) and Visit 2 to Visit 6.

Results of

Statistical Analysis Plan  
Test product: Revacept  
EudraCT number: 2011-001006-10  
Date 10.06.2019

- vital signs
  - Weight
  - Blood pressure systolic and diastolic (right arm / left arm)

will be summarized by visit by means of descriptive statistics. Change from baseline in weight, heart rate, systolic and diastolic blood pressure will be summarized by means of statistics and compared between treatment groups using the Wilcoxon test.

### **8.5.2 Physical examination**

Physical examination was assessed at Screening (Visit 1, Baseline) and Visit 2 to Visit 6.

Results of assessment of

- heart
- lung
- abdomen
- oedema

will be described presenting number and percent of patients with abnormal findings at post-baseline visits and with normal values at baseline (Screening, Visit 1) and summarized by means of frequency tables.

### **8.5.3 ECG parameters**

ECG parameters which were assessed at Screening (Visit 1, Baseline), Visit 3, Visit 5 and Visit 6 are heart rate, type of rhythm, clinically significant ST-segment deviation and interval times.

Results for

- Heart rate [beats/minute]

will be summarized by means of descriptive statistics

- Type of rhythm
  - Sinus rhythms
  - Atrial fibrillation
  - Other rhythm

will be summarized by means of frequency tables

- Clinically significant ST-segment deviation

will be summarized by means of frequency tables

- Interval times

Statistical Analysis Plan  
Test product: Revacept  
EudraCT number: 2011-001006-10  
Date 10.06.2019

- P [ms]
- PQ interval [ms]
- QRS complex [ms]
- QTc [ms]

will be summarized by means of descriptive statistics

Change from baseline in heart rate, and interval times will be summarized by means of statistics and compared between treatment groups.

#### **8.5.4 Adverse events**

Adverse events will be categorised by primary system organ class (SOC) and MedDRA preferred term (PT) as coded using the MedDRA dictionary.

- The inquiries for AEs will be summarised with respect to the type of inquiry
  - Patient showed up for follow up visit and AE/SAE was reported during a follow up visit
  - Patient did not show up for follow-up visit and AE/SAE was reported by telephone or in writing with
    - the patient
    - a family member
    - an attending physician
    - another person
- An overview table will be presented with the number (and percentage) of patients with at least one AE, with at least one SAE, with AEs leading to treatment discontinuation and with drug-related AEs.
- The number (%) of patients with at least one AE will be presented in frequency tables by adverse events as reported.

#### **8.5.5 Laboratory results**

The following endpoints will be evaluated exploratory using descriptive methods of statistics. Generated p-values will be interpreted in an explorative way.

- Laboratory results
  - Biochemistry
  - Haematology
  - Coagulation
  - Urinalysis
- Bleeding

- Reduction in haemoglobin level
  - by at least 20 g/L
  - by at least 50 g/L
  - of  $\geq 2$  units of blood
  - of  $\geq 4$  units of blood
- Requiring transfusion
  - of  $\geq 2$  units of blood
  - of  $\geq 4$  units of blood
- Symptomatic bleeding in a critical area of organ
  - Intra-ocular
  - Intra-spiral
  - Intra-musculär
  - Retro-peritoneal
  - Intra-articular
  - Pericardial
  - Subdural intra-cranial
  - Intra-cerebral
- Other symptomatic bleeding
  - Gastrointestinal
  - Other organ
- Involving hypotension
- Surgery necessary
- Fatal

### **8.5.6 Pharmacokinetics**

Analyses of anti drug antibodies and Revacept pharmacokinetics will be conducted at the AdvanceCor GmbH according to validated protocols and SOPs effective at that moment in time.

## **8.6 Change in concomitant medication**

- Change in concomitant medication will be described presenting
  - number and percent of patients with new concomitant medication - taken first time after start of treatment (during the course of the study)
  - number and percent of patients with changes of pre-existing concomitant medication according to
    - dose increased
    - dose decreased
    - discontinued
  - type of medication

Statistical Analysis Plan  
Test product: Revacept  
EudraCT number: 2011-001006-10  
Date 10.06.2019

- type of medication by indication  
and summarized by means of frequency tables.

- Change in concomitant rescue medication with anti-platelet or anti-thrombotic effects.

## **8.7 Individual patient listing**

Individual patient listings will be produced for all raw data and a selection of the derived data. Listings will be ordered by treatment group, and by gender and study centre within treatment group.

